C. Early Stage, Non-Small Cell, Lung Cancer Cases: The table below includes number of patients from 2007 with stage I and II, non-small cell lung cancer entered in each local cancer registry. These data only include patients with tissue proven diagnoses and not those who had CT lesions with extremely high cancer probability and refused surgery or dropped out of follow-up (we did include these patients in our prospective study). Therefore, eligible patients are underestimated while "percent surgery" rates are overestimated when factoring in all patients with early stage, non-small cell disease.

Site	Number of Cases	African-Americans	Percent Surgery
ECU	63	11	70
MCHS	141	24	69
UNC	57	14	74
USC	66	17	75

From our prospective study, we anticipate an average recruitment rate of 70% across sites. Only 11% of all patients approached during the post-diagnosis – pre-treatment recruiting interval refused participation and there was no difference by race.

D. Retrospective Chart Review: Our recently completed study demonstrated that co-morbid

conditions differentially affected black patients' care. Given these data, during the first six months of the intervention trial we will perform a retrospective chart review for the 2008 and 2009 calendar years. We will review all patients diagnosed with stage I or II, non-small cell cancer to serve as a baseline for surgical rates and to examine outcomes of patients treated with and without surgery using a very specific analysis of co-morbid conditions and severity. These data will be checked against Strand's report [45] to assess compatibility and level of detail. The results will be used by our expert panel of co-investigators and site investigators to create an educational checklist to remind lung cancer providers that surgical contra-indications are often relative and subjective. We anticipate the availability of approximately 100-150 charts per site in the 2-year pre-study window. Charts will be selected using appropriate ICD-9 billing codes. Data will be collected in an aggregate manner and no linkage files or specific patient identifiers will be maintained.

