E. Prospective Study: All sites will begin recruiting patients by the beginning of study Month 13. As most cancer programs have at least rudimentary patient tracking and navigation, this degree of usual care will serve as the control. All providers will receive the co-morbid illness educational checklist at all sites and will receive monthly data concerning surgical rates by comorbid condition and race. Patients will be randomized to either usual care or a more intense communication intervention delivered by a trained cancer communication educator as described below. Since we are building on the methods of our prior cohort study, pretesting of recruitment methods and study instruments can proceed quickly before randomization. Lung cancer surgery rates in the control groups will be compared to historical controls at the individual sites to account for a passive effect of the registry and educational checklist. As care registries and data compilation by race is a mandate of the HITECH portion of the American Recovery and Reinvestment Act, we don't believe that it's ethical to deny any group access to the registry. Given the flat rate of lung cancer surgery and persisting racial gap documented for over a decade in datasets of national scope [7, 36, 38], historical controls for this portion of the study are justified.

1. Inclusion and Exclusion Criteria for Patients

We will enroll patients who meet these criteria: (1) age 21 years or greater; (2) a probability of 60% or higher of a lung lesion being malignant as calculated by Bayesian analysis derived from clinical and radiographic criteria or, alternatively, biopsy proven disease; and (3) the patient has received a clinical classification of stage I or II disease. By "clinically classified", we mean using all studies including CT scans, PET scans, bone scans, mediastinoscopy, and / or any study or procedure performed short of thoracotomy.

We will exclude patients from this study for 3 reasons: (1) incarceration / ward of the state status, (2) severe cognitive impairment, (3) absolute contraindications by pulmonary function testing, or (4) Non-English speaking. Hispanic patients represent less than 4 percent of lung cancer patients in North Carolina restricting our ability to document an intervention effect.

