We will analyze patient level cross-sectional dichotomous outcome data using logistic regression growth models. We will both limit analyses to the cancer communicator control group and do an all enrollee analysis by adding a communicator intervention / no communicator intervention predictor variable to the models. First, we will fit a saturated growth model to estimate annual proportions of these outcomes, before and after the registry/feedback intervention, to assess the effects of the intervention on these outcomes by contrasting the proportions before and after the interventions. We will test the null hypothesis that the proportions before and after the intervention are the same. We will repeat this analysis by including "race" and "race x time" interaction in this model to examine changes in these outcomes between the two races and also if there are any differential changes over time. We will test the null hypothesis that the proportions before and after the intervention are the same for each race

Data interpretation: If our data feedback / registry intervention is found to produce an effect in less than the 4 Cancer Centers, it will prompt further examination of the factors that moderate or mediate the relationship between the intervention and completion of cancer treatment. Thus, by conducting an embedded randomized cohort-control study of the Cancer Communicator intervention component, we may be better able to provide more information about the dimensions along which these interventions can or cannot be generalized.

hypothesis 2c. a cancer communicator who utilizes active listening and teach-back methods during discussions about lung cancer surgery with newly diagnosed, early stage patients will increase the rate of surgery in African-American patients more than Caucasian patients compared to usual care.

We will compare post intervention, unadjusted, surgical rates between African-American and White lung cancer patients using chi-square analysis as discussed under Aim 1. We will also perform the maximum rate analysis stratified by race. The regression models described above under Aim 1. We will also apply these analyses to patients in the communicator group alone selecting patients on an intention to treat basis.

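### The chart-review baseline and the prospective cohort follow different eligibility rules, so the non-randomised before/after surgery rates may differ through case definition alone

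*Protocol*

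**What the plan says.** **Baseline.** Protocol section D states: "We will review all patients diagnosed with stage I or II, non-small cell cancer to serve as a baseline for surgical rates". It covers calendar years 2008 and 2009. On case finding it says "Charts will be selected using appropriate ICD-9 billing codes", without naming the codes or saying whether a tissue diagnosis is needed. It expects "approximately 100-150 charts per site in the 2-year pre-study window" and adds: "Data will be collected in an aggregate manner and no linkage files or specific patient identifiers will be maintained". No exclusion is listed, and the section does not say whether stage is clinical or pathological.

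**Prospective cohort.** Protocol section E.1 requires clinical stage I or II disease and either biopsy proof or "a probability of 60% or higher of a lung lesion being malignant". It confirms that enrolment does not depend on tissue. The exclusions include "absolute contraindications by pulmonary function testing", along with severe cognitive impairment, incarceration or ward status, and not speaking English.

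**Comparisons that join the two.** Protocol section E sets the control arm against each site's historical controls. SAP section 6 has a Pearson chi-square of pre- against post-intervention rates (in the text under hypothesis 1b). For hypotheses 2a and 2b it plans growth models: "We will test the null hypothesis that the proportions before and after the intervention are the same", overall and then for each race. Aim 3 examines rates before and after. The SAP does not name the source of the earlier rates; I take it to be the chart review because Protocol section A assigns the baseline to it.

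**The concern.** A before/after comparison isolates the registry, feedback and checklist only if both periods count the same kind of patient. Here at least two differences in the rules are tied to the outcome.

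- Patients with an absolute lung-function contraindication would rarely be resected. They stay in the chart denominator and are removed from the prospective one, which makes the later rate look higher.
- Some patients with a probable but unproven lesion decline surgery because the diagnosis is uncertain, as Protocol section E.1 notes. They are enrolled prospectively. If charts are found through a diagnosis that needs tissue, they are missing from the baseline, while similar patients diagnosed at operation are included. That makes the later rate look lower.

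Hypotheses 2a and 2b have no randomised comparison to fall back on, because Protocol section E.4.B delivers provider feedback at every site. Historical controls are defended in section E by flat surgery rates over a decade. That answers secular trend, not case definition.

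**Working it through.** **1. The plan's own figure.** SAP section 7 uses a one-sample test with N = 496, p0 = 0.63, p1 = 0.69 and alpha 0.05. Two-sided:

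- Null standard error: √(0.63×0.37/496) = 0.02168. Alternative: √(0.69×0.31/496) = 0.02077.
- Power = Φ[(0.06 − 1.96×0.02168)/0.02077] = Φ(0.843) = 0.80.

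This reproduces. Its reference rate is the previous prospective study, not the chart review, so it does not depend on this point.

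**2. Effect of unexcluded contraindications.** Inputs: a true rate of 63% among trial-eligible patients in both periods (borrowed from SAP section 7), no real effect, and a share c of charts that are unoperated patients with absolute contraindications. The documents give no value for c; 5 to 15% is an assumed range. Apparent baseline = 0.63 × (1 − c).

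The next columns give the chance that a two-sided 5% chi-square rejects. Chart numbers are 4 sites × 100 = 400. The prospective number is 496 for all enrollees, or 248 for controls if allocation is 1:1 (assumption).

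| c | Apparent baseline | Spurious gain (points) | Rejects, 400 vs 496 | Rejects, 400 vs 248 |
|---|---|---|---|---|
| 0 | 63.0% | 0 | 5% | 5% |
| 5% | 59.85% | 3.15 | 16.2% | 12.5% |
| 10% | 56.7% | 6.3 | 48.2% | 35.3% |
| 15% | 53.55% | 9.45 | 81.5% | 65.8% |

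Worked entry for c = 10%, 400 vs 496:

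- Pooled rate: (400×0.567 + 496×0.63)/896 = 0.6019.
- Pooled standard error: √[0.6019×0.3981×(1/400 + 1/496)] = 0.0329. The unpooled value is also 0.0329.
- Φ[(0.063 − 1.96×0.0329)/0.0329] = Φ(−0.045) = 0.48.

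**3. Both mechanisms together.** Let u be the share of the prospective-type population that has no tissue diagnosis, is not operated on and is absent from the charts. Baseline = 0.63 × (1 − c)/(1 − u).

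| u | c | Baseline | After minus before (points) | Rejects, 400 vs 496 |
|---|---|---|---|---|
| 10% | 0 | 70.0% | −7.0 | 59.6% |
| 10% | 5% | 66.5% | −3.5 | 19.2% |
| 10% | 10% | 63.0% | 0 | 5% |
| 5% | 10% | 59.7% | +3.3 | 17.4% |

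The two cancel only when u = c. All values of u and c are assumptions. The tables show that either sign is possible; they do not predict one.

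**The case against.** **Partial control exists.** Protocol section A says baseline rates will account for race and co-morbid illness, section D plans detailed co-morbidity abstraction, and Aim 3 adjusts for the Aim 1 variables. This stands as partial control. It cannot restore patients missing from the charts, several Aim 1 covariates (trust, satisfaction, perceptions of communication) are interview measures that charts are unlikely to hold, and the pre/post chi-square is unadjusted.

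**The tissue restriction is inferred for the charts.** The protocol's warning that surgery "rates are overestimated when factoring in all patients with early stage, non-small cell disease" is about the 2007 cancer-registry table in section C. Section D is a separate data set with no stated tissue rule. This stands: the second mechanism is a possibility to be settled. The absence of the lung-function and other exclusions needs no such inference.

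**A reader might take the size of the bias from section C.** The pooled 2007 registry rate is (63×0.70 + 141×0.69 + 57×0.74 + 66×0.75)/327 = 233.07/327 = 71.3%, which is 8.3 points above the 63% of the previous study. The arithmetic is right, but neither figure comes from the chart review or the new cohort. The gap also mixes calendar year, consent and race mix, and the table states no 4-month window. It should not be used as an estimate of the bias. Nor should it be judged against the 6-point increase in SAP section 7: that benchmark belongs to a comparison with the previous prospective study, which section C says did include high-probability lesions without tissue.

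**A reader might also infer that the before/after rates must differ, or that the trial's main result is compromised.** Neither follows. The mechanisms oppose each other and could cancel. The randomised comparison of communicator with usual care (hypotheses 1a and 2c) applies one set of criteria to both arms.

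**Racial differences.** Hypotheses 2a and 2b concern the gap between races. The race-by-time term is distorted mainly if the mismatch differs by race, and the documents give no figure on that. The planned before/after test within each race is exposed directly.

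**Conclusion.** The concern holds for the non-randomised comparisons: control arm against historical controls, the pre/post chi-square, hypotheses 2a and 2b, and the before/after part of Aim 3. The two periods use different eligibility rules that bear on the outcome, no section aligns them, and the planned adjustment is only partial. A change could be produced or hidden by case definition alone.

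The size is not known. Under assumed shares of 5 to 15% unoperated contraindicated charts, a 63% rate and no offsetting loss of patients without tissue, the spurious gain is about 3 to 9 points. With an offsetting loss, it could be nil or reversed. The conclusion rests on reading the chart review as the source of the pre-intervention rates and on section D meaning what it says about including all diagnosed cases.

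**What to change.** Before abstraction:

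1. Record for each chart, de-identified and at patient level instead of in aggregate: lung-function contraindication, clinical stage, the other trial exclusions, and the basis and timing of diagnosis. The aggregate-only wording in Protocol section D would have to change. It already sits badly with the patient-level growth models in SAP section 6.
2. Apply the trial's exclusions and clinical-stage rule to the charts for every before/after comparison.
3. State whether cases diagnosed clinically, without tissue, enter the baseline.
4. Pre-specify a sensitivity analysis restricted in both periods to patients with a tissue diagnosis before resection, and report patients enrolled on probability alone separately. This should not be the primary set, because it drops the patients described in section E.1 who go to surgery without prior tissue.

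The cost is a few extra fields in charts that are already being abstracted for co-morbidity, a smaller baseline set, and fewer prospective patients in the sensitivity analysis. The change does not remove differences due to consent or to the planned oversampling of black patients, which should be acknowledged when the results are interpreted.

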- D. Co-morbidity educational checklist – The co-morbidity check list will be designed to address the seeming over interpretation of co-morbid states in decisions against surgery by African-American patients or their physicians (II and VII). Derived from the retrospective chart review, this checklist will be used to help inform physicians' decisions in patients who do not have absolute contra-indications for surgery. Overall results of the retrospective chart review will be delivered at the beginning of designated MTOP conferences at each study site or at a mutually agreeable meeting that includes the whole lung cancer care team. For African-American study patients randomized to intervention who are identified as having dropped out of care per the definition in section 1, the most recent physician in the specific patient's chain of care, will be given that patient's co-morbidity list via the CCE. This list will serve as a reminder that decisions for African-American patients have been different and will be designed to attenuate the subjective use of co-morbid states to justify decisions against lung resection surgery.

5. *Outcome Measures*

Primary Outcome. Whether or not patients undergo lung resection surgery represents the main study outcome. We will conform to the 4 month standard used in the SEER database. To ascertain the result, we will first call patients' physicians to determine whether surgery occurred within the designated time frame. Given the possibility that individual patients could seek other opinions and receive surgical care elsewhere, when appropriate, we will ask the patient, or a family member (if the patient is dead or unavailable), whether surgery was performed by someone other than the index physician. If surgery has not occurred, we will ask for reasons. Through appropriate consent, we will retain the option of confirmatory medical records review. For secondary analyses, we will record surgeries that occur beyond the 4 month threshold.

Secondary Outcomes.

1. One year, post-enrollment survival in surgical and non-surgical groups
2. Satisfaction of patients that received interventions compared to those who did not
3. Patients' perceptions of communication for those patients that received intervention compared to those who did not
4. SF-12 scores at baseline, 6 months post-enrollment and 12 months post enrollment

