Lung Cancer Surgery: Decisions Against Life Saving Care - The Intervention

NCT01687738

Protocol Date: May 13, 2011

Most Recent IRB Approval Date: March 29, 2016

Lung Cancer Surgery: Decisions Against Life Saving Care - The Intervention

STATISTICAL ANALYSES

Outcome Measures

Primary Outcome. Whether or not patients undergo lung resection surgery represents the main study outcome. We will conform to the 4 month standard used in the SEER database. To ascertain the result, we will first call patients' physicians to determine whether surgery occurred within the designated time frame. Given the possibility that individual patients could seek other opinions and receive surgical care elsewhere, when appropriate, we will ask the patient, or a family member (if the patient is dead or unavailable), whether surgery was performed by someone other than the index physician. If surgery has not occurred, we will ask for reasons. Through appropriate consent, we will retain the option of confirmatory medical records review. For secondary analyses, we will record surgeries that occur beyond the 4 month threshold.

Secondary Outcomes.

1. One year, post-enrollment survival in surgical and non-surgical groups
2. Satisfaction of patients that received interventions compared to those who did not
3. Patients' perceptions of communication for those patients that received intervention compared to those who did not
4. SF-12 scores at baseline, 6 months post-enrollment and 12 months post enrollment

6. Data Analysis:

Our current plan includes:

Descriptive statistics (means, standard deviations, frequencies, proportions, correlations, and graphical displays) will be computed for all study variables at baseline and post-baseline. The distribution of all outcome variables will be assessed to determine if distributional assumptions are valid. Descriptive statistics will be obtained for all the variables overall and by race and site. Statistical methods for addressing each of the specific aims of the study are detailed in this section. Since several statistical tests are planned, there is the possibility of incurring spurious results if we do not correct for multiple comparisons. All tests are based on a 2-sided alpha of 0.05.

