
hypothesis 1b. the communication intervention will be more effective in patients who score lower in measures of health literacy

Using the logistic regression analyses for clustered data as noted above, the interaction effects of health literacy, S-TOFHLA scores, and intervention group will be tested in all models. . S-TOFHLA scores will be tested as a continuous variable and also, separately, as a dichotomous variable comparing those categorized as inadequate or marginal literacy with those categorized as adequate literacy [103]. Cumulative pre-intervention surgical rates will be compared at all sites with post-intervention rates using Pearson's chi-square test. Post-intervention rates will be compared using test of proportions and changes in proportions from baseline will be compared between surgical and nonsurgical groups using appropriate methods. To determine if the post-intervention rate approaches maximal surgical rates, we will identify patients with high risk co-morbidities, above the age of 80, and need for pneumonectomy or multiple lobectomy in the "no surgery group", subtract this sum from the denominator then re-calculate the surgical rate. We will analyze the secondary specific aim, To measure the effect of the intervention on patients' perceptions of communication and satisfaction with care, by dichotomizing these variables and replacing surgery as the dependent variable in chi-square and logistic regression models as described under the specific aim above.

Specific Aim 2. To reduce the documented difference in lung resection surgery and mortality between African-American and White patients with early stage, non-small cell

lung cancer.

hypothesis 2a. giving physicians who make lung cancer surgery decisions data relating co-morbidity to surgical outcomes will reduce racial differences in surgery

hypothesis 2b. using a real time lung cancer registry to provide physicians race-specific feedback about their surgical treatment of early stage lung cancer patients will reduce racial differences in surgery

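### The before/after surgical rates are not measured the same way: the chart baseline has no stated time window and no enquiry about surgery elsewhere, so historical comparisons mix measurement with effect by an unknown amount and sign

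*Protocol*

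**What the plan says.** **Before.** Protocol section D (Retrospective Chart Review) covers calendar years 2008 and 2009: "We will review all patients diagnosed with stage I or II, non-small cell cancer to serve as a baseline for surgical rates". On selection it says "Charts will be selected using appropriate ICD-9 billing codes", and on size "We anticipate the availability of approximately 100-150 charts per site in the 2-year pre-study window". On the form of the data: "Data will be collected in an aggregate manner and no linkage files or specific patient identifiers will be maintained". The section does not say within what time surgery must occur, from what date time is counted, or how an operation done elsewhere would be found.

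**After.** The primary outcome (Protocol section E.5; SAP, Outcome Measures) is lung resection, with the rule "We will conform to the 4 month standard used in the SEER database". The study team calls the physician first. When appropriate it then asks the patient or a family member "whether surgery was performed by someone other than the index physician". Later operations are kept apart: "For secondary analyses, we will record surgeries that occur beyond the 4 month threshold". The 12-month interview text in Protocol section E.3 counts the 4 months from diagnosis.

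**Comparison.** Protocol section E compares the control arm with historical controls at each site. The SAP text under hypothesis 1b says "Cumulative pre-intervention surgical rates will be compared at all sites with post-intervention rates", by Pearson chi-square. SAP Aim 2 contrasts proportions before and after the registry and feedback for hypotheses 2a and 2b, and Aim 3 uses before and after surgery rates.

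**The concern.** A before/after contrast estimates an effect only if the outcome is found and counted in the same way in both periods. Here the after period has a time limit and an active search for outside surgery. The before period has no stated limit, and a review that keeps no identifiers cannot make such a search.

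Two errors follow, in opposite directions. Baseline surgery done elsewhere and absent from the site chart lowers the before rate and creates a false rise. Baseline surgery after 4 months, if counted, raises the before rate and hides a real rise.

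The stakes are highest for hypotheses 2a and 2b. Every provider at every site receives the checklist and feedback, so no concurrent group goes without them and the historical contrast is the only test. Protocol section E justifies historical controls by flat national rates. That argument concerns secular trend and does not cover a change in how surgery is ascertained. If delay or outside surgery differs by race, the estimated change in the racial gap is distorted as well.

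**Working it through.** **1. The plan's own figure.** SAP section 7 uses a one-sample test with 496 patients, p0 = 0.63, p1 = 0.69 and two-sided 0.05:

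N = [(1.96·√(0.63·0.37) + 0.842·√(0.69·0.31)) / 0.06]² = 495.5, with power 80.0% at 496.

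The figure reproduces. Its comparator is the previous study, not the 2008-2009 charts, so the chart rule does not enter it.

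**2. Drift with no true change.** Let S be the true share ever resected, E the share of resections missing from the site chart because they were done elsewhere, and L the share done after 4 months. Suppose the charts are read without a window and the prospective enquiry finds everything. Then:

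- before = S(1 − E)
- after = S(1 − L)
- after − before = S(E − L)

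The documents give neither E nor L, so the values below are assumptions. With S = 0.63:

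| E | L | Drift (points) |
|---|---|---|
| 5% | 5% | 0 |
| 5% | 0 | +3.2 |
| 0 | 5% | −3.2 |
| 10% | 5% | +3.1 |
| 5% | 10% | −3.1 |
| 10% | 0 | +6.3 |
| 0 | 10% | −6.3 |

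A drift of 6 points needs E − L = 0.06/0.63 = 9.5% of all resections.

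**3. Effect on the chi-square when surgery is missed.** Section D's 100-150 charts at each of 4 sites give 400-600; take 500, against 496 enrolled. With E = 5% and L = 0, before = 0.63 × 0.95 = 0.5985 and after = 0.63, a difference of 0.0315. The pooled rate is 0.614 and its standard error is √(0.614·0.386·(1/500 + 1/496)) = 0.0308. The two-sided rejection probability is Φ(0.0315/0.0308 − 1.96) plus a negligible lower tail, about 18%, against a nominal 5%.

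| Missed elsewhere (L = 0) | False rise (points) | Rejection, 496 vs 500 | Rejection, 248 controls vs 500 |
|---|---|---|---|
| 3% | 1.9 | 9% | 8% |
| 5% | 3.2 | 18% | 13% |
| 10% | 6.3 | 53% | 38% |

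The last column applies to control-only comparisons and assumes 1:1 allocation (496/2 = 248). At E = 5%, 400-600 charts against 496 gives 16-19%.

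**4. Effect when late surgery is counted.** Hold the true 4-month rate at 63%, so the unwindowed chart rate is 0.63/(1 − L). For L = 3%, 5% and 10% this is 64.9%, 66.3% and 70.0%. With 500 charts against 496 enrolled, the chi-square has 52% power for a true rise from 63% to 69% under matched measurement. That falls to 27%, 15% and 6%.

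**5. Race.** Take the previous-study rates in SAP section 7 (0.55 black, 0.66 white). A net 5% in one group only would move the apparent gap by 0.55 × 0.05 = 2.75 points or 0.66 × 0.05 = 3.3 points. This too is an assumption; the documents do not say whether the shares differ by race.

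**The case against.** The strongest reply is that section D is silent on the window but does not set a contrary rule. The SAP places its outcome definition ahead of all the aims, and Aim 2 refers to the same outcomes before and after. An analyst could reasonably apply 4 months to the charts. This stands. A reader might infer that the plan lays down a baseline with no time limit, but the documents do not say so. If the window were the only gap, this would be a request for missing detail.

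It does not answer the ascertainment difference. Patients behind a review without identifiers cannot be called, whatever window is used.

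Other points also stand in part:

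- The two errors oppose each other and may cancel. Exact cancellation needs E = L, which nothing in the documents supports or excludes.
- Surgery by a different physician in the same system would be in the chart, and outside surgery may be noted there. E could be small. Nothing shows that late or outside surgery was common.
- Data kept in aggregate are not necessarily beyond a window, because a time split made at abstraction would be usable. SAP Aim 2 even speaks of patient-level data. What cannot be relied on is adding the split after abstraction with no linkage file.
- A chart-based rule for enrolled patients adds work, because the plan relies first on calls. It is feasible: the registry in Protocol section E.4 tracks procedures, and section E.5 keeps the option of records review.

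**Conclusion.** The concern holds for the historical comparisons: control arm versus historical controls, the pre/post chi-square, hypotheses 2a/2b and the before/after part of Aim 3. As written, each mixes a change of measurement with any effect, by an amount and sign that the documents do not fix. The 3-point false rise and 18% rejection (13% for about 248 controls) rest on an assumed true rate of 63%, 500 charts and a net 5% missed. They show sensitivity and are not estimates.

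Two stronger readings are not supported. One is that measurement alone could produce the 6-point difference in SAP section 7. That would need about 9.5% of resections misclassified on balance in one direction, a share the documents do not give, and the 6 points belong to the comparison with the previous study. The other is that the main trial result is biased. Hypothesis 1a compares randomised arms under one stated rule and is unaffected, as is the stated power.

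The change should be made, and before abstraction, because an unsplit baseline without linkage may not be repairable afterwards.

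**What to change.** **Protocol section D.** Before abstraction, add a field that splits baseline surgery into within 4 months of diagnosis, later, and none, tabulated by race and co-morbidity. State how the start date is set when there is no tissue diagnosis before surgery, since section E.1 enrols such patients, and use that rule in both periods.

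**SAP Aims 1 to 3 and Protocol section E.** For every before/after comparison, count in both periods only surgery within 4 months that is documented in the site chart or registry. Leave out prospective operations known only from patient or family report, including any entered in the registry on that basis alone. Keep the full ascertainment for the randomised comparison, and report the fully ascertained prospective rate separately beside the before/after rate.

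**Cost.** A little more abstraction work, a check of the source of each prospective operation, and a slightly lower before/after rate. One imbalance may remain: the registry exists only in the after period, so documentation may be more complete then. This should be stated as a limitation.
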